8.3 Adverse Events and Serious Adverse Events

Adverse event and SAE definitions are provided in [Appendix 3](#).

All AEs (serious and nonserious) reported by the participant must be recorded on the source documents and eCRF provided by the Sponsor. Medical terminology should be used for AE reporting. Adverse events should be reported as a single unifying diagnosis whenever possible or, in the absence of a unifying diagnosis, as individual signs or symptoms.

The Investigator and any qualified designees are responsible for detecting, documenting, and recording events that meet the definition of an AE or SAE and remain responsible for following up AEs that are serious, considered related to the study intervention or study procedures, or that caused the participant to discontinue the study intervention (see Section 7).

8.3.1 Time Period and Frequency for Collecting Adverse Event and Serious Adverse Event Information

All AEs and SAEs will be collected from the signing of the ICF until the EOS; AEs and SAEs that are ongoing at the EOS should be monitored until resolution or 30 days after EOS, whichever is shorter (see [Section 1.3](#)).

Medical occurrences that begin before the start of study intervention but after obtaining informed consent will be recorded on the Medical History/Current Medical Conditions section of the eCRF, not the AE section.

All SAEs will be recorded and reported to the Sponsor or designee immediately and under no circumstance should this exceed 24 hours, as indicated in [Appendix 3](#). The Investigator will submit any updated SAE data to the Sponsor within 24 hours of it being available.

Investigators are not obligated to actively seek information about AEs or SAEs after conclusion of study participation. However, if the Investigator learns of any SAE, including a death, at any time after a participant has been discharged from the study, and he/she considers the event to be reasonably related to the study intervention or study participation, the Investigator must promptly notify the Sponsor.

8.3.2 Method of Detecting Adverse Events and Serious Adverse Events

The method of recording, evaluating, and assessing causality of AE and SAE and the procedures for completing and transmitting SAE reports are provided in [Appendix 3](#).

Care will be taken not to introduce bias when detecting AEs and/or SAEs. Open-ended and nonleading verbal questioning of the participant is the preferred method to inquire about AE occurrences. For example, participants should be asked the nonleading question: “How have you felt since your last visit?”

Exacerbation or disease progression should be reported as an AE only if there are unusual or severe clinical features that were not present, or experienced earlier, or not expected based on the course of the condition.

In addition, the Sponsor must be notified immediately by telephone, fax, or e-mail of any immediately reportable events. Immediately reportable events (IRE) include the following:

- SAEs
- Pregnancies. Although normal pregnancy is not an AE, it will mandate study intervention discontinuation and must be reported on an IRE form and the Pregnancy Surveillance Form(s) to the Sponsor. Pregnancy will only be documented on the AE eCRF if there is an abnormality or complication. This includes pregnancy of the participant or the participant’s partner

Adverse event, start date, end date, seriousness, severity, relationship to study intervention, action taken with study treatment and outcome will be recorded on the source documents and in

the eCRF. Special attention should be paid to recording hospitalization and concomitant medications.

8.3.3 Follow-up of Adverse Events and Serious Adverse Events

Nonserious AEs that are identified at any time during the study must be recorded on the AE eCRF with the current status (ongoing or resolved/recovered) noted. All nonserious events (that are not IREs) that are ongoing at the last scheduled contact will be recorded as ongoing on the eCRF. For any AE having been identified throughout the study, additional relevant medical history information may be requested by the Sponsor during analysis to further ascertain causality (including, but not limited to, information such as risk-related behavior, family history and occupation).

After the initial AE/SAE report, the Investigator is required to proactively follow each participant at subsequent visits/contacts. All AEs and SAEs will be collected from the signing of the ICF until the EOS; AEs and SAEs that are ongoing at the EOS should be monitored until resolution, stabilization, until the event is otherwise explained, the participant is lost to follow-up or 30 days after EOS, whichever is shorter (Section 1.3).

Resolution means that the participant has returned to the baseline state of health and stabilized means that the Investigator does not expect any further improvement or worsening of the participant's condition. The Investigator will continue to report any significant follow-up information to the Sponsor up to the point the event has resolved or stabilized, or the participant is lost to follow-up, or has died.

Further information on follow-up procedures is provided in [Appendix 3](#).

8.3.4 Regulatory Reporting Requirements for Serious Adverse Events

Prompt notification by the Investigator to the Sponsor of a SAE is essential so that legal obligations and ethical responsibilities towards the safety of participants and the safety of a study intervention under clinical investigation are met.

The Sponsor has a legal responsibility to notify both the local regulatory authority and other regulatory agencies about the safety of a study intervention under clinical investigation. The Sponsor will comply with country-specific regulatory requirements relating to safety reporting to the regulatory authority, Institutional Review Boards (IRB)/Independent Ethics Committees (IEC), and Investigators.

Investigator safety reports must be prepared for suspected unexpected serious adverse reactions (SUSAR) according to local regulatory requirements and Sponsor policy and forwarded to Investigators as necessary.

An Investigator who receives an Investigator safety report describing a SAE or other specific safety information (eg, summary or listing of SAEs) from the Sponsor will review and then file it along with the Investigator's Brochure and will notify the IRB/IEC, if appropriate according to local requirements.

8.3.5 Pregnancy

Details of all pregnancies in female participants and female partners of male participants will be collected after the start of study intervention and until 90 days after the last dose of study intervention.

If a pregnancy is reported, the Investigator should inform the Sponsor within 24 hours of learning of the pregnancy and should follow the procedures outlined in [Appendix 4](#).

Abnormal pregnancy outcomes (eg, spontaneous abortion, fetal death, stillbirth, congenital anomalies, ectopic pregnancy) are considered SAEs.

8.4 Treatment of Overdose

Standard symptomatic support measures should be used in the case of excessive pharmacological effects or overdose. No antidotes are available.

8.5 Pharmacokinetics

For all participants, serial blood samples will be drawn prior to each VIS649/placebo IV infusion and at the end of each infusion in order to determine circulating serum concentrations of VIS649, as specified in [Table 1](#) and [Table 5](#). Up to 60 participants (approximately 15 participants in each cohort) may have a more intensive PK and PD sampling schedule, as described in [Table 5](#). Study participants who agree to participate in this more intensive PK and PD sample collection sub-study will sign an additional informed consent for this activity.

Instructions for the collection and handling of biological samples will be provided by the Sponsor in a separate laboratory manual. The actual date and time (24-hour clock time) of each sample will be recorded.

Samples collected for analyses of serum VIS649 concentration may also be used to evaluate safety or efficacy aspects related to concerns arising during or after the study.

Drug concentration information that may unblind the study will not be reported to investigative sites or blinded personnel until the study has been unblinded.

Table 5: Pharmacokinetic and Serum Immunoglobulin Sampling Schedule

Time relative to infusion	Day 1			Day 3	Day 8	Day 15
	Pre infusion (-30 min)	Post infusion (±15 min)	2h (±15 min)	48h (±1 day)	168h (±1 day)	336h (±3 days)
Month 0	PK+Ig	PK only	PK only	PK only	PK+Ig	PK+Ig
Month 1	PK+Ig	PK only				PK+Ig
Month 2	PK+Ig	PK only				PK+Ig
Month 3	PK+Ig	PK only				PK+Ig
Months 4-10	PK+Ig	PK only				
Month 11	PK+Ig	PK only	PK only	PK only	PK+Ig	PK+Ig
Month 12	PK+Ig ¹					PK+Ig
Month 13	PK+Ig ¹					PK+Ig
Month 14	PK+Ig ¹					PK+Ig
Month 15	PK+Ig ¹					

Abbreviations: IG = immunoglobulin; PK = pharmacokinetics.

Note: postinfusion times are relative to the end of infusion.

¹ No infusion on this date; therefore, only 1 sample to be obtained.

8.6 Pharmacodynamics

Serial blood samples will be drawn in order to determine serum IgA, IgG, and IgM concentrations as well as the following analytes for exploratory PD endpoints [REDACTED]

[REDACTED] Up to 60 participants (approximately 15 participants in each cohort) will have a more intensive total serum IgA/IgM/IgG sampling schedule, as described in Table 5. Study participants who agree to participate in this more intensive sample collection sub-study will sign an additional informed consent for this activity.

It is expected that VIS649 will result in obvious reductions in serum IgA and IgM, which, if visible to site and Sponsor staff at the participant level, would effectively unblind treatment assignment. Participant level unblinded Ig data will not be available for review by the site or Sponsor staff. Unblinded Ig data will be routinely reviewed by the DSMB as part of the scheduled, if required, ad hoc safety reviews (see Section 9.6). Additional PK/PD summaries will be provided at an aggregate level in accordance with planned interim analyses (see Section 9.5).

8.7 Genetics

A DNA sample will be collected to evaluate host DNA genetic markers related to IgAN susceptibility loci, the APRIL/B-cell activating factor pathway, and/or immunity in consenting subjects. Blood samples will be taken on Day 1 predose.

8.8 Biomarkers

Collection of samples for other biomarker research is also part of this study. Participation is optional; a separate informed consent must be obtained. Participants who do not wish to

participate in the biomarker research may still participate in the study. [REDACTED]

[REDACTED]

[REDACTED]

Samples will be tested to assess the exploratory objectives listed in Section 3.

[REDACTED]

Samples may be stored in de-identified fashion for a maximum of 15 years (or according to local regulations) following the last participant's last visit for the study to enable further analysis of biomarker responses.

8.9 Immunogenicity Assessments

Antibodies to VIS649 will be evaluated in serum samples collected from all participants at the visits outlined in Table 1. Additionally, serum samples should also be collected at the final visit from participants who discontinued study intervention or were withdrawn from the study. These samples will be tested by the Sponsor or Sponsor's designee.

Serum samples will be screened for antibodies binding to VIS649 and the titer of confirmed positive samples will be reported. Other analyses may be performed to evaluate the stability of antibodies to VIS649 and/or further characterize the immunogenicity of VIS649.

The detection and characterization of antibodies to VIS649 will be performed using a validated assay method by or under the supervision of the Sponsor. All samples collected for detection of antibodies to VIS649 will also be evaluated for VIS649 serum concentration to enable interpretation of the antibody data. Antibodies may be further characterized and/or evaluated for their ability to neutralize VIS649 activity. Samples may be stored for a maximum of 15 years (or according to local regulations) following the last participant's last visit for the study at a facility selected by the Sponsor to enable further analysis of immune responses to VIS649. This analysis may be provided in a separate report.

8.10 Medical Resource Utilization and Health Economics

Not applicable

9. STATISTICAL CONSIDERATIONS

9.1 Statistical Hypothesis

The primary efficacy objective of this study is to evaluate the effect of VIS649 on proteinuria. The hypothesis that there is a VIS649-related dose response in the change from baseline in natural log uPCR at Month 12 versus placebo will be formally tested.

9.2 Sample Size Determination

A sample size of 144 participants, randomly assigned in a 1:1:1:1 schema to VIS649 2, 4, or 8 mg/kg, or placebo, would provide sufficient power at 80% to detect a significant linear dose response relationship given a standard deviation of 0.49, and an assumed difference in uPCR reduction, for instance 15%, 30%, and 45%, between VIS649 2, 4, or 8 mg/kg and placebo, respectively. The study-wide type I error rate is a 2-sided alpha of 0.05. This sample size would account for a dropout rate of ~20%.

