9.5 Interim Analysis

In addition to five DSMB safety reviews ([Section 9.6](#)), three PK/Ig analyses and one interim efficacy analysis are planned:

- The first PK/Ig analysis will be performed when approximately 25% of participants have been randomized and have completed 3 months of study dosing. All the PK/Ig assessments will be performed by a separate, unblinded team. Summarized results will be made available to the study Sponsor for planning of future studies.
- The second PK/Ig analysis will be performed when approximately 20 participants have been randomized and have completed 9 months of study dosing. This analysis will be used to update previously developed population PK/PD models. Summarized results will be made available to the study Sponsor for planning of future studies.
- The third PK/Ig analysis will be performed when approximately 50% of the participants have been randomized and have completed 6 months of study dosing and approximately 20 participants have completed 12 months of study dosing. Summarized results will be made available to the study Sponsor for planning of future studies.
- An interim efficacy analysis will be performed at the time of the fourth scheduled DSMB meeting (when 50% of randomized participants have completed 6 months of study dosing and approximately 20 participants have completed 12 months of study dosing). Group-unblinded efficacy summaries (with individual participant treatment blinded) will be prepared for Sponsor review to inform future study design.
- The interim efficacy analysis will not include hypothesis testing and will be for the purpose of future study design and planning. The primary efficacy endpoint, change in proteinuria levels from baseline, will be analyzed. No modifications to this study protocol are planned based on results of the interim analyses.

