### **3. GENERAL STATISTICAL METHODS**

#### **3.1. Sample Size Justification**

The sample size for this study was calculated assuming a linear dose response (reduction of uPCR) of 0%, 15%, 30%, and 45% in placebo and VIS649 2, 4, and 8 mg/kg groups, respectively. Applying contrasts of -3, -1, 1, and 3 for the corresponding dose levels and analyzing uPCR on the natural log scale, the result is an expected mean change from baseline of 0, -0.163, -0.357, and -0.593 for placebo and VIS649 groups of 2, 4, and 8 mg/kg, respectively. Using an analysis of variance model with contrasts of -3, -1, 1, and 3 for the corresponding groups, a standard deviation (SD) of 0.87, 80% power, a 2-sided type I error rate of 0.05, and accounting for a dropout rate of ~ 20%, the required sample size is 36 participants per group, or 144 participants overall.

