#### 4.3.1. Primary Efficacy Analyses

The primary endpoint of this study is the change from baseline in uPCR (Schedule A) on the natural log scale at Month 12 (Days 360) (See [Section 3.4](#) for change from baseline on the natural log scale equation).

A Mixed Model with Repeated Measurements (MMRM) will be used to compare the change from baseline in uPCR (Schedule A visits Months 9 and 12) on the natural log scale between treatment groups. The response variable of the MMRM is the change from baseline in uPCR (Schedule A) on the natural log scale. The model includes the fixed effects of treatment group, categorical visit (Months 9 and 12), strata and a treatment-by-visit interaction, with a fixed effect covariate of baseline uPCR (Schedule A) on natural log scale. An unstructured covariance matrix will be used. If the model does not converge, then the Toeplitz covariance structure will be used.

From the MMRM, the following statistics will be produced: 1) the least-square mean (LSM), its corresponding standard error (SE), and 95% confidence interval (CI) for each treatment group; 2) the geometric mean ratio calculated by exponentiated (LSM) and 95% CI for each treatment group; 3) the least-square mean difference (LSMD) between treatment groups using placebo as reference, its corresponding SE and 95% CI and p-value for testing the LSMD; and 4) the treatment difference expressed as geometric mean reduction calculated as  $(1 - \text{exponentiated LSMD}) \times 100\%$ , and 95% CI.

The geometric mean reduction and corresponding SE estimated from the MMRM for each treatment group will also be presented graphically.

The alpha value for the primary efficacy analyses (ie, p-value for the test of linear contrast at Month 12) will be adjusted to account for one review of the efficacy endpoint during the interim analyses. Although the interim efficacy data reviews will not include hypothesis testing ([Section 4.8.1](#)), the type I error rate for the primary endpoint will be reduced by 0.002 for the interim efficacy review, resulting in a 2-sided type I error rate of 0.048 for the linear contrast p-value. A p-value < 0.048 for the linear contrast of the primary efficacy analysis will support a claim of efficacy.

The primary efficacy analysis result also includes the p-value from the linear contrast statement of -3, -1, 1, and 3 evaluated for VIS649 dose levels 0 (placebo), 2, 4, and 8 mg/kg, respectively at Month 12.

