## **5. CHANGES TO PLANNED ANALYSES**

This document is amended after the formal efficacy interim analyses as outlined in [Section 4.8](#). Sponsor was unblinded to the group summary of the efficacy interim results.

Additional analysis populations, secondary and exploratory endpoints and time points for analyses are included in this SAP.

The major change between protocol and this SAP is summarized below:

1. There are 2 planned interim efficacy analyses in the protocol. Sponsor chose not to perform the interim efficacy 1 during the trial. In this SAP, [Section 4.8.1](#) is updated to reflect the new scope and analysis method for the interim efficacy analysis.

All other changes from procedures outlined in this SAP will be summarized in the study report.

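### Protocol 9.2 pairs SD 0.49 with 80% power for the linear dose response, but its own inputs give about 99.8%; SAP 3.1 reaches the same 144 participants and 80% with SD 0.87

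*Protocol*

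**What the plan says.** Protocol 9.1 sets the hypothesis and the scale: a "dose response in the change from baseline in natural log uPCR at Month 12 versus placebo will be formally tested". Protocol 9.2 then justifies 144 participants, allocated equally to placebo and 2, 4 and 8 mg/kg. It says this number "would provide sufficient power at 80% to detect a significant linear dose response relationship given a standard deviation of 0.49", with uPCR reductions against placebo of, for example, 15%, 30% and 45%. Alpha is two-sided 0.05, and dropout of about 20% is said to be covered. No contrast weights are given.

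SAP 3.1 makes the same justification in more detail. It uses the same reductions, contrast weights -3, -1, 1, 3, and log-scale means of 0, -0.163, -0.357 and -0.593. It then uses "a standard deviation (SD) of 0.87, 80% power, a 2-sided type I error rate of 0.05" and about 20% dropout, and concludes that "the required sample size is 36 participants per group, or 144 participants overall".

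SAP 4.3.1 lowers the level of the test itself after the interim review, "resulting in a 2-sided type I error rate of 0.048 for the linear contrast p-value". SAP section 5, which lists the major change from the protocol, does not mention the SD.

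**The concern.** Required sample size for a fixed contrast, effect, alpha and power is proportional to the variance. The two SDs differ by a factor of 0.87/0.49 = 1.78, so the variances differ by a factor of 3.15. Two documents with identical effects, alpha, power and dropout cannot both arrive at 36 per arm from those two SDs.

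The power statement is what justifies the size of the trial, and it shapes how a negative primary result is read. Someone who takes SD 0.49 at face value and works through it would see a non-significant linear contrast as strong evidence against the assumed dose response (a miss rate of about 0.2%). Under the SAP's SD the miss rate is about 1 in 5. Protocol 2.1 says that later development will build on this study, so the SD may also be carried forward into later planning.

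**Working it through.** **Inputs.** Log means for reductions of 0, 15, 30 and 45%: 0, ln 0.85 = -0.1625, ln 0.70 = -0.3567, ln 0.55 = -0.5978 (Protocol 9.1 for the scale, 9.2 for the reductions). Contrast -3, -1, 1, 3 (SAP 3.1). Evaluable per arm: 36 × 0.8 = 28.8 for a full 20% loss, or 36/1.2 = 30 if dropout was allowed for by multiplying by 1.2.

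**Formulae.** L = Σcμ; SE = SD·√(Σc²/n) with Σc² = 20; δ = |L|/SE. Power is taken from the noncentral t with 4n - 4 degrees of freedom, or from the normal approximation Φ(δ - 1.960). Below, t and z mark which was used.

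|L| = 3(0.5978) + 0.3567 - 0.1625 = 1.988. With the SAP's rounded means, |L| = 1.973. Ranges cover both sets of means.

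**The SAP figure (SD 0.87).** At n = 30, SE = 0.87·√(20/30) = 0.710 and δ = 1.988/0.710 = 2.80.

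| Evaluable per arm | Power at alpha 0.05 | Power at alpha 0.048 |
|---|---|---|
| 30 | 78.7–79.2% (t), 79.3–79.9% (z) | 78.1–78.7% (t), 78.8–79.4% (z) |
| 28.8 | 77.0–77.6% (t), 77.7–78.3% (z) | 76.4–77.0% (t), 77.2–77.8% (z) |

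The n for 80% power is 30.1–30.5 (z) or 30.6–31.0 (t). So 30 evaluable, and 30 × 1.2 = 36 per arm, roughly reproduces.

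**The protocol figure (SD 0.49).** At n = 28.8, SE = 0.49·√(20/28.8) = 0.408 and δ = 1.988/0.408 = 4.87. Power is 99.77–99.79% (t). At n = 30 it is 99.83–99.85%. The stated 80% is not reproduced.

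**What 80% would require at SD 0.49.**
- Sample size by z: n = (1.960 + 0.842)² × 20 × 0.49² / 1.988² = 9.5 (9.7 with the SAP means). By t: 10.1–10.2. So 10 to 11 evaluable per arm. Dividing by 0.8 gives 12.5 and 13.75, so 13 to 14 randomised per arm, or 52 to 56 in total.
- Effect size: keeping 144 participants, the log effects would have to shrink to 0.58 (n = 28.8) or 0.57 (n = 30) of those assumed. That means reductions of about 9%, 18–19% and 29%.

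**Other readings of the protocol sentence, at 28.8 per arm.**
- Coefficients spaced by dose (-3.5, -1.5, 0.5, 4.5): 99.8%.
- 0.49 read as a variance (SD 0.70): 91.8–92.2%.
- Reductions left untransformed (0, 0.15, 0.30, 0.45): 95.4%, or 94.7% with dose spacing.

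**A calculation that does fit.** A pairwise test of a 30% reduction against placebo at SD 0.49 needs n = 2 × (1.960 + 0.842)² × 0.49² / 0.3567² = 29.6, so 30 per arm (80.5% power by z, 79.2% by t), and 30 × 1.2 = 36. This is an inference about where 0.49 came from, and it is not the test that Protocol 9.2 names.

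**The case against.** Five points can be made for the plan.

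- **The printed power is about right.** If 0.87 is the planning value, the true figure is 77% to 80%, and a reader who sees only the 80% is not misled. This stands in part. It makes the protocol's SD the wrong element, but the sentence is still wrong as written, and the SD is the part most likely to be reused.
- **80% may be meant as a floor, and the reductions are only examples.** A floor does not explain 144, since 52 to 56 randomised would meet it. The reductions are the only effects given, and the SAP uses the same ones.
- **The documents may not be a matched pair.** The SAP says "There are 2 planned interim efficacy analyses in the protocol", whereas this protocol says that "three PK/Ig analyses and one interim efficacy analysis are planned". The SAP also has about 100 sites and a Month 16 visit, against about 80 sites and Month 15 here. An SD changed between versions could explain two values. It cannot explain 0.49 paired with 80% inside one sentence of one document.
- **76% to 79% is too fine a restatement.** The primary model is an MMRM with a baseline covariate and Month 9 data, so a simple analysis of completers may understate power, and dropout is only approximate. This is fair. The figures follow SAP 3.1's own analysis-of-variance method, and it is why the SD should be labelled raw or baseline-adjusted.
- **The pairwise origin is selective.** It takes the middle effect, the normal approximation and a 1.2 multiplier. By t, or by dividing by 0.8, it gives 38 per arm. That also stands, so it is offered only as a possibility for the sponsor to confirm.

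**Conclusion.** The point holds. The SD and the power in Protocol 9.2 do not go together for the linear dose-response test: the stated inputs give about 99.8%, some 20 percentage points above the 80% claimed. The result rests on the log scale of Protocol 9.1, about 20% dropout and a one-way comparison of four arms. It does not depend on whether the contrast is equally spaced or spaced by dose. SAP 3.1, with SD 0.87, is close to its stated 80% and is not materially wrong. The documents do not show which SD is the intended planning value. The fault lies in the sample-size justification only. The test, the sample size and the decision rule are unchanged.

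**What to change.** Change the wording in Protocol 9.2 and SAP 3.1, and add no participants.

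1. Use one planning SD for the log change in both places, give its source, and say whether it is raw or baseline-adjusted.
2. Restate the power of the linear contrast to match, at the 0.048 level used for the test. If 0.87: about 76–78% after a full 20% dropout, or about 78–79% with 30 evaluable per arm. If 0.49: over 99%. Do not quote power for full follow-up unless the effect assumed after stopping treatment is also stated.
3. If 0.49 and 36 per arm came from a pairwise comparison, name that comparison in place of the linear dose response.
4. If the SD changed between this protocol and the version that the SAP follows, say so in the SAP.

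Optionally, correct the SAP's 8 mg/kg log mean from -0.593 to ln(0.55) = -0.598. This moves the power by about half a percentage point.

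The cost is text only. Under SD 0.87 the plan gives up a round 80% for a figure a few points lower.
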